6.1.2 Secondary evaluation criteria

- Functional assessment using the DALLAS Self-Assessment Questionnaire (French version of the DRAD validated by the S.F.R. Spine Section) completed at the start of treatment (1st session) and at the end of treatment (5th session);
- Assessment of Quality of Life using the SF-12 Quality of Life questionnaire (short form) completed at the start of treatment (1st session) and at the end of treatment (5th session);
- Psychological assessment using the STAI Y questionnaire (Spielberg's State-Trait Anxiety Inventory). The STAI YA measuring the state of anxiety is completed at the beginning and end of each session. The STAI YB measuring trait anxiety is completed at the start of treatment (1st session) and at the end of treatment (5th session).
- Any changes in the usual/current use of medication (analgesics and psychotropic drugs) prescribed for low back pain, by collecting information at each session.

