Comparisons between randomisation groups will be made systematically (1) without adjustment (2) by adjusting for factors whose distribution could be unbalanced between groups.

All statistical tests will be carried out with a risk of error of the first kind α of 5%.

Part of the analyses concerning the secondary evaluation criteria should be mainly exploratory in nature. As discussed by several authors (*Bender, R.; Lange, S. Adjusting for multiple testing-When and how? J. Clin. Epidemiol. 2001, 54, 343-349; Feise, R.J. Do multiple outcome measures require p-value adjustment? BMC Med. Res. Methodol. 2002, 2, 8; Rothman, K.J. No adjustments are needed for multiple comparisons. Epidemiology 1990, 1, 43-46*), adjustment for the risk of error of 1st kind will not be proposed systematically, but on a case-by-case basis in the light of clinical and not purely statistical considerations.

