9.1.3 Secondary analyses

The analyses described above for the primary endpoint will be supplemented in a multivariate situation by a mixed linear regression model to take into account the covariates selected on the basis of the results of the univariate analysis and their clinical relevance. The practitioner effect will be measured and taken into account in the statistical analyses as a random effect. The results will be expressed in terms of regression coefficient and 95% confidence interval.

Comparisons between randomisation groups (group receiving only conventional massophysiotherapy, group receiving both conventional masso-physiotherapy and fasciatherapy and group receiving only fasciatherapy) concerning quantitative assessment criteria (functional assessment by the DALLAS self-assessment questionnaire, quality of life assessment by the SF-12 quality of life questionnaire, psychological assessment by the STAI Y questionnaire) will be carried out by Student's t-test or non-parametric Mann-Whitney test if the test conditions are met, assessment of quality of life using the SF-12 quality of life questionnaire, psychological assessment using the STAI Y questionnaire) will be carried out using Student's t test or the non-parametric Mann-Whitney test if the conditions of Student's test are not met (normality verified by the Shapiro-Wilk test and equality of variances by the Fisher-Snedecor test). Particular attention will be paid to the statistical distributions of the quantitative data under study. Where appropriate, the above analyses may be supplemented by more appropriate generalised linear regressions. The results will be expressed in terms of effect size and 95% confidence interval. In line with the recommendations proposed by Vickers and Altman, an ANCOVA-type analysis will also be proposed in order to compare the scores at the 5th session by adjusting for the values at the 1st session.

The STAI YB measuring anxiety status will be completed at the beginning and end of each session; the statistical analysis will therefore follow the same statistical analysis plan as that described for the primary endpoint.

Comparisons between the randomisation groups (conventional physiotherapy-only group, conventional physiotherapy and fasciatherapy group and fasciatherapy-only group) for categorical variables (e.g. functional assessment scores, quality of life assessment scores and psychological

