assessment scores, categorised according to the statistical distribution or thresholds commonly reported in the literature) will be performed by chi-square test or Fisher's exact test. The results will be expressed in terms of absolute difference and 95% confidence interval. In multivariate situations, mixed generalized linear regression models (logit link function) will be considered. The results will then be expressed in terms of relative risk and 95% confidence interval.

Concerning the longitudinal analysis of categorical parameters (for example pain and STAI YB categorised according to statistical distribution or thresholds reported in the literature), the analysis will consider a mixed model approach for repeated data of the generalised linear type (logit link function for a binary dependent variable) making it possible to study the fixed effects of group, assessment time (session) and their interaction, while taking into account inter and intra patient variability (subject taken as a random effect), in addition to the (random) practitioner effect. The results will be expressed in terms of odds ratios and 95% confidence intervals.

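### Section 9.1.3 gives the each-session anxiety model to STAI YB when the form collected each session is STAI YA, and labels the results of a logit-link model as relative risks (secondary analyses only)

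*Combined protocol and SAP*

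**What the plan says.** **Anxiety forms.** Section 6.1.2 defines two forms with different schedules. For state anxiety: "The STAI YA measuring the state of anxiety is completed at the beginning and end of each session". For trait anxiety: "The STAI YB measuring trait anxiety is completed at the start of treatment (1st session) and at the end of treatment (5th session".

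Section 9.1.3 then says: "The STAI YB measuring anxiety status will be completed at the beginning and end of each session". It draws an analysis decision from this: "the statistical analysis will therefore follow the same statistical analysis plan as that described for the primary endpoint". Later in 9.1.3, the paragraph on longitudinal analysis of categorical parameters gives as its example "pain and STAI YB categorised according to statistical distribution or thresholds reported in the literature". The same section also covers both forms generically, as "psychological assessment by the STAI Y questionnaire", with between-group tests and an ANCOVA to "compare the scores at the 5th session by adjusting for the values at the 1st session".

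**Effect measure.** For categorical variables in multivariate situations, section 9.1.3 plans mixed generalised linear models with a logit link and says the results will be given as relative risks with 95% confidence intervals. The next paragraph uses the same link for the longitudinal categorical analysis and gives the results as odds ratios.

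**Status of these analyses.** Section 9.1.1 says: "Part of the analyses concerning the secondary evaluation criteria should be mainly exploratory in nature".

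**The concern.** The two statements about when STAI YB is completed cannot both be true. The slip also carries an instruction, because the choice of model follows from the stated schedule. Taken literally with section 6.1.2, the session-by-session model is assigned to a form that has no data at sessions 2 to 4, while the form that is collected at every session has no model named for it. Anxiety is one of the aspects listed in the secondary objectives (section 3.2), so the plan should name the variable it models.

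The second statement attaches a measure to a model whose direct output is a different measure. If the exponentiated logit coefficient were reported under the label given, readers would take an odds ratio for a relative risk. When the outcome is common, that overstates the effect, whether it is a benefit or a harm.

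**Working it through.** **1. Can each form support the planned model?** Section 9.1.2 models the variation in pain before and after each of the 5 sessions, with group, session and their interaction as fixed effects. Section 9.1.3 carries that plan over to the anxiety form it names. From the schedules in section 6.1.2:

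| Form | Readings per patient | Before/after pairs | Sessions with data |
|---|---|---|---|
| STAI YA (state) | 5 sessions × 2 = 10 | 5 | 1 to 5 |
| STAI YB (trait) | 1 + 1 = 2 | 0 | 1 and 5 |

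Only YA supplies a within-session change at each session. Section 9.1.3 describes the form it names as measuring anxiety status and as completed at every session. Both features match YA in section 6.1.2 and neither matches YB. The letter is therefore what is wrong, in both places where it appears.

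**2. Is YB left without an analysis?** No. The generic STAI Y wording in 9.1.3, with tests between groups and a session-5 comparison adjusted for session 1, fits YB's two readings. Because that wording covers both forms, however, it does not say which analysis is meant for which form.

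**3. How far apart are the two effect measures?** The documents give no event rates, so the control risks p0 below are assumptions. With p1 = RR × p0, the formula is OR = [p1/(1 − p1)] / [p0/(1 − p0)].

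| Assumed p0 | OR when RR = 1.40 | OR when RR = 0.60 |
|---|---|---|
| 10% | (0.14/0.86)/(0.10/0.90) = 1.47 | (0.06/0.94)/(0.10/0.90) = 0.57 |
| 30% | (0.42/0.58)/(0.30/0.70) = 1.69 | (0.18/0.82)/(0.30/0.70) = 0.51 |
| 50% | (0.70/0.30)/(0.50/0.50) = 2.33 | (0.30/0.70)/(0.50/0.50) = 0.43 |

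In the reverse direction, an odds ratio of 2.0 corresponds to relative risks of 1.82, 1.54 and 1.33 at the same three control risks.

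**4. Would the outcomes be common here?** Section 9.1.3 allows scores to be cut by their statistical distribution or by published thresholds. If the first meant a split at the overall median (an assumption), the three arms, planned at equal size, would average 50%, so their proportions would sum to 1.5. Two examples:

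- Arms at 45%, 45% and 60%: RR = 0.60/0.45 = 1.33; OR = (0.60/0.40)/(0.45/0.55) = 1.83.
- Arms at 40%, 40% and 70%: RR = 0.70/0.40 = 1.75; OR = (0.70/0.30)/(0.40/0.60) = 3.50.

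Prevalence under published thresholds is unknown.

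**5. Reach.** The primary analysis (section 9.1.2) is a mixed model for pain reported as regression coefficients, and the sample size (section 9.2) uses neither STAI nor a binary outcome. No stated figure in the plan changes.

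**The case against.** On the anxiety form, the best defence is that this is a labelling slip the documents themselves resolve. The construct and the schedule both point to YA, the second mention is only an example, and an analyst holding two YB readings per patient could not fit the before/after model to them. No wrong result is shown to follow. That is fair as to consequence. It does not make the text right: the letter is wrong twice, an analysis choice hangs on it, and YA appears nowhere in section 9.

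On the effect measure, relative risks can be derived from a logit mixed model, so naming one is not impossible, and nothing says the raw coefficient will be relabelled. The model is only to be considered. The same scores are also analysed as continuous measures, and the simple categorical comparison reports an absolute difference. All of this stands, and it limits the weight of the point. But no derivation step is given, and the measure stated is not the one the model yields directly.

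The figures in step 3 are also open to criticism, and that criticism stands too. They use assumed risks and crude two-group odds, whereas the planned model would return an adjusted odds ratio conditional on its random effects. They show that the measures diverge; they do not estimate the size of an error in this trial.

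**Conclusion.** Both points hold. The STAI label in section 9.1.3 contradicts section 6.1.2 in two places. As written, it assigns a model of within-session change to a form with no within-session pairs (2 readings per patient, against 10 readings and 5 pairs for YA). This rests on the documents alone.

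The relative-risk label does not match the direct output of the logit model. The size of any resulting misstatement depends on event rates that the documents do not give. On the assumed risks it runs from slight at 10% (1.47 against 1.40) to large at 50% (2.33 against 1.40).

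Only secondary analyses are affected, and the plan calls part of them mainly exploratory. The corrections are worth making because they are simple and unambiguous, not because the trial's main conclusion depends on them.

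**What to change.** - **Anxiety form:** in section 9.1.3, replace STAI YB with STAI YA both in the sentence on each-session completion and in the longitudinal categorical example. Add a clause saying that YB is analysed by the between-group tests and the session-5 ANCOVA adjusted for session 1, which the section already contains.
- **Effect measure:** report odds ratios with 95% confidence intervals from the logit mixed model, as the following paragraph does. If a relative risk is wanted, state how it and its interval are obtained, for example from standardised predicted risks, and how the random effects are handled.

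The cost is two labels and one clause for the first point, and two words (or one sentence for the alternative) for the second. No additional data or patients are needed, and section 9.3 allows the analysis plan to be revised. If the analysis has already been run, the report should say which STAI form was modelled and how any relative risk was derived.

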9.1.4 Method for taking into account missing, unused or invalid data

A sensitivity analysis will be carried out to study the attrition bias, i.e. the quantity (level of attrition) and nature (independence from the randomisation group) of the missing data, and to propose the most appropriate data imputation method if necessary.

9.2 Justification of the number of subjects / power analysis.

In order to evaluate the specific benefits of fasciatherapy compared with physiotherapy for chronic low back pain in terms of variation in pain before and after each of the 5 sessions considered in this protocol, the estimate of numbers is based on recruitment capacity, the time required for experimentation and simulations concerning the effect size for risks of error of 1st and 2nd kind fixed respectively at 1.7% (two-sided with correction for multiple comparisons: group receiving only conventional physiotherapy, group receiving conventional physiotherapy and fasciatherapy) and less than 20%.

Thus, if we estimate that a clinically relevant difference in pain assessment is between 1 and 2 points, for a standard deviation of the variation in pain of 1.5 to 2.5 points, we should include 30 to 40 patients for a statistical power of over 80% and an intra-individual correlation coefficient (5 sessions per subject) conventionally set at 0.5.

This proposal must be revised upwards in order to take into account the dropouts inherent in this type of protocol and the inter- and intra-practitioner variability (due to the experimental design of the cluster trial) which can be measured by the intra-class correlation coefficient and which it seems reasonable to estimate in the context of this project to be of the order of 0.05 to 0.2. It is therefore proposed to include 60 patients in each of the study groups.

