7.3 Description of the general logistical organisation of the trial

Practitioners will receive an observation booklet by post. Each practitioner will include between 3 and 5 patients in the study.

The promoter is responsible for gathering all the data collected at each phase of the study and at the end of the study. They will compile the data into an Excel file and transmit it to the statistician.

- 7.4 Inclusion criteria for practitioners
 - Qualified physiotherapist,
 - Private practice,
 - Having a mixed practice combining conventional physiotherapy and fasciatherapy which is outside the scope of conventional practice,
 - Having completed at least 105 hours of training in fasciatherapy.

8 Data collected

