9.1.2 Main analysis

In order to evaluate the specific benefits of fasciatherapy compared with physiotherapy for chronic low back pain in terms of variation in pain before and after each of the 5 sessions considered in this protocol, the main analysis will consider a mixed model approach for repeated data, making it possible to study the fixed group effects (group receiving only conventional physiotherapy, group receiving both conventional physiotherapy and fasciatherapy and group receiving fasciatherapy only), assessment time (session) and their interaction, while taking into account inter- and intrapatient variability (subject taken as a random effect), in addition to the (random) practitioner effect. The results will be expressed in terms of regression coefficient and 95% confidence interval. It will also be proposed to study the difference between randomisation groups for each of the sessions. The results will be expressed in terms of effect size and 95% confidence interval.

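### Section 9.2 ties over 80% power to differences of 1 to 2 points and SDs of 1.5 to 2.5, but 60 patients per group generally do not deliver it for 1 point at SD 2 to 2.5

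*Combined protocol and SAP*

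**What the plan says.** Section 9.2 sets two-sided alpha at 1.7%, corrected for the comparisons among three groups, and a type II error below 20%. It supposes that "a clinically relevant difference in pain assessment is between 1 and 2 points". The spread it allows for is given by the words "for a standard deviation of the variation in pain of 1.5 to 2.5 points", and the correlation between a patient's 5 sessions is set at 0.5. From these it concludes that "we should include 30 to 40 patients for a statistical power of over 80" per cent. The simulations are mentioned but not shown, and the text does not say whether 30 to 40 is per group or in total.

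The section continues: "This proposal must be revised upwards in order to take into account the dropouts inherent in this type of protocol", and also for variability between practitioners, with an intra-class correlation of about 0.05 to 0.2. No dropout rate or design effect is given. The result is: "It is therefore proposed to include 60 patients in each of the study groups". Cluster size comes from section 7.3: "Each practitioner will include between 3 and 5 patients in the study".

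**The concern.** The required number varies with the square of SD divided by difference. From 2 points at SD 1.5 to 1 point at SD 2.5 that ratio rises from 0.75 to 2.5, so the required number rises (2.5/0.75)² = 11-fold. A span of 30 to 40 cannot serve the whole of that range, yet section 9.2 attaches over 80% power to it without restriction.

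The corner at risk matters because 1 point is the plan's own lower limit of clinical relevance. Someone interpreting a small or null result would infer from section 9.2 that a true 1-point difference had more than an 80% chance of detection at any stated SD. The stake is the stated sensitivity of the design, not the validity of the analysis.

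**Working it through.** **Inputs.** From section 9.2: two-sided alpha 0.017 (z = 2.387), power 80% (z = 0.842), difference d = 1 to 2, SD = 1.5 to 2.5, 5 sessions with correlation 0.5, practitioner ICC 0.05 to 0.2, and 60 per group. From section 7.3: m = 3 to 5 patients per practitioner. Two readings are assumed: 30 to 40 is per group, and the ICC applies to patient means. A total of 30 to 40 would make the shortfall larger.

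**Step 1: the 30 to 40 figure, before clustering.** Giving full credit for averaging 5 sessions, the variance factor is (1 + 4 × 0.5)/5 = 0.6. Then n per group = 2 × (2.387 + 0.842)² × SD² × 0.6 / d². For example, at d = 1 and SD 2: 2 × 10.42 × 4 × 0.6 / 1 = 50.0.

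| n per group | SD 1.5 | SD 2 | SD 2.5 |
|---|---|---|---|
| 1 point | 28.1 | 50.0 | 78.2 |
| 1.5 points | 12.5 | 22.2 | 34.7 |
| 2 points | 7.0 | 12.5 | 19.5 |

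The plan's figure reproduces at 1 point with SD 1.5 (29 rounded up) and at 1.5 points with SD 2.5 (35). Forty per group is enough in 7 of the 9 cells. It is not enough for 1 point at SD 2 (51 rounded up; power with 40 is 69%) or at SD 2.5 (79; power 47%).

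**Step 2: the step to 60.** Design effect DE = 1 + (m − 1) × ICC.

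- Favourable: m = 3, ICC 0.05, DE = 1.10, effective n = 60/1.10 = 54.5
- Middle: m = 4, ICC 0.125, DE = 1.375, effective n = 43.6
- Adverse: m = 5, ICC 0.2, DE = 1.80, effective n = 33.3

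Taking 35 as the mid-range base, 35 × 1.375 = 48.1, so 60 covers mid-range inputs with some room for dropout. At the upper end, 40 × 1.80 = 72, which exceeds 60 before any dropout.

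**Step 3: power at 60 per group, no dropout, adverse to favourable clustering.**

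| | SD 1.5 | SD 2 | SD 2.5 |
|---|---|---|---|
| 1 point | 87% to 98% | 60% to 84% | 39% to 62% |
| 1.5 points | over 99% | 94% to over 99% | 78% to 95% |
| 2 points | over 99% | over 99% | 97% to over 99% |

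So 6 of 9 cells exceed 80% at the adverse end and 8 of 9 at the favourable end. With middle clustering, 1 point has 95%, 73% and 51%.

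For 1 point at SD 2.5, even 60 unclustered patients with no dropout give only 67%. For 1 point at SD 2, the effective n must reach 50.03, so DE must stay below 60/50.03 = 1.2 with no dropout. At ICC 0.05 that means fewer than 5 patients per practitioner. With 10% dropout, even DE = 1.10 leaves 54/1.10 = 49.1, and power is 79%.

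**Step 4: checks.**

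- A simulated t-test on practitioner means (20,000 runs, alpha 1.7%) gave, for 1 point with adverse, middle and favourable clustering, 56%, 70% and 82% at SD 2, and 35%, 48% and 60% at SD 2.5. These are about 2 to 4 points below the formula.
- At the 5% level that section 9.1.1 sets for all tests ("All statistical tests will be carried out with a risk of error of the first kind"), 1 point at SD 2.5 still has only 56% to 77%.

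**Step 5: detectable difference at 80% power.** d = 3.229 × √(2 × 0.6 × SD² × DE / n), with n = 60 × (1 − dropout) and DE from 1.10 to 1.80. The plan gives no dropout rate, so three are assumed.

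| Assumed dropout | SD 1.5 | SD 2 | SD 2.5 |
|---|---|---|---|
| 0% | 0.72 to 0.92 | 0.96 to 1.23 | 1.20 to 1.53 |
| 10% | 0.76 to 0.97 | 1.01 to 1.29 | 1.26 to 1.61 |
| 20% | 0.80 to 1.03 | 1.07 to 1.37 | 1.34 to 1.71 |

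**The case against.** The best defence is that section 9.2 never says every pairing exceeds 80%. It gives an output range for input ranges, some pairings do reproduce 30 to 40, the number also rests on recruitment capacity and time, and no power is restated after the rise to 60. On that view the figure is under-labelled rather than miscalculated. This stands in part, since the plan's figure is right for certain pairings. But the text neither names those pairings nor restricts the statement, so a reader cannot know that the lower difference is covered only at the smaller SDs.

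A second defence is the model. A baseline-adjusted analysis of all 5 sessions, with variance factor 0.35, would give 86% to 98% for 1 point at SD 2 with 60 per group and clustering. Section 9.2 describes no such adjustment, its SD is already that of the change in pain, and the main model in section 9.1.2 lists only group, session and their interaction as fixed effects. Even then, 1 point at SD 2.5 reaches 65% to 87%, which is not assured. The SD 2 shortfall is thus somewhat model-dependent, and the SD 2.5 shortfall much less so. In the other direction, the between-group comparisons at each session that section 9.1.2 also plans get no credit for averaging. One point would then need 84 per group at SD 2 and 131 at SD 2.5 before clustering.

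Third, the favourable end is optimistic. Three patients per practitioner implies 60 practitioners for 180 patients, whereas section 11.4 reports 49 willing and 41 able to include such patients, or 180/49 = 3.7 to 180/41 = 4.4 each. At ICC 0.05 the upper limits for 1 point fall from 84% to about 81% to 83% (SD 2) and from 62% to about 59% to 61% (SD 2.5). This is correct, and it does not help the plan.

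**Conclusion.** The concern holds. Over 80% power is a fair description of most of the stated range, and 60 per group is a defensible size for mid-range inputs. It is not a fair description for 1 point at SD 2.5, where 60 per group falls short at every stated ICC and cluster size, nor generally for 1 point at SD 2, which passes only with very little clustering and dropout.

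This rests on averaging 5 sessions at correlation 0.5, an ICC acting on patient means, 30 to 40 read as per group, and a normal approximation that is slightly generous with 12 to 20 practitioners per group. Estimates and tests are unaffected: section 9.1.2 states "The results will be expressed in terms of regression coefficient and 95% confidence interval", and those intervals will still show which differences the data exclude. What is wrong is the stated sensitivity, and it is worth correcting.

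**What to change.** Keep 60 per group and restate section 9.2 as detectable differences. Possible wording, with 10% dropout as a placeholder assumption: *With 60 patients per group, 3 to 5 per practitioner, practitioner ICC 0.05 to 0.2, two-sided alpha 1.7% and 10% dropout, the trial has 80% power for a difference of about 0.8 to 1.0 point at SD 1.5, 1.0 to 1.3 at SD 2 and 1.3 to 1.6 at SD 2.5.* The sponsor should put in its own dropout rate and update the figures. A t calculation on practitioner means moves the adverse end at SD 2.5 to about 1.7, and the sponsor may prefer that more cautious value.

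The paragraph should also say that 30 to 40 is per group, name the difference/SD pair it rests on, show the design effect that leads to 60, and drop the implication of over 80% power for 1 point at SD 2 to 2.5.

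The cost is one rewritten paragraph, with no extra patients and no change to the analysis. The sensitivity claimed at SD 2 to 2.5 becomes less favourable.
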